### *Non-competitive selection of eligible patients*

Upon screening log completion, the sites will proceed through the patients listed in the screening log and will select all consecutive patients who meet the inclusion criteria (Section 8.2.1) and none of the exclusion criteria (Section 8.2.2), starting with patients who received their first Ozurdex injection the closest to 1 January 2015. Patient selection will not be competitive between countries and will stop when the quotas of eligible patients has been reached in each country, i.e. approximately 70 patients in Germany and 30 patients in Switzerland. Consent from patients will not be requested; as the study is retrospective and anonymized, a waiver of consent will have been requested from the Ethics Committees.

### *Competitive selection of patients - patients who are naïve to anti-VEGF treatment*

During the patient selection process, special attention will be given to patients that are naïve to anti-VEGF treatment prior to first Ozurdex implant injection [REDACTED]

[REDACTED], and sites will be asked to do their best to select a predetermined number of patients who do not meet this exclusion criteria. Recruitment of patients that are naïve to anti-VEGF treatment will stop when approximately 50 patients have been selected in Germany and Switzerland.

[figure not shown]
Overall, patient selection will stop when 150 patients have been selected for the study. The number of patients included at each site, in particular the number of patients that are naïve to anti-VEGF treatment, will be chosen based on feasibility surveys and consultations with the Sponsor.

---

 1 September 2017 was chosen to get at least 1 year of follow-up data on 1 September 2018 for all selected patients.

[figure not shown]

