### 8.2 Patients

From a public health and market access perspective, the present study population constitutes a broader real-world patient population than that reflected in clinical trials. The present study design cannot make any conclusions on causal relationships, but can rather explore real-world Ozurdex drug utilization patterns, effectiveness and safety. It is expected that the results from this study may be generalizable to the overall population presenting with DME and treated with Ozurdex in Germany and Switzerland.

Patients may contribute at most one eye into the study. If both eyes meet the inclusion criteria, the eye that received the most Ozurdex injections will be chosen as the study eye.

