## **9.0 DESCRIPTION OF THE ELIGIBLE SCREENING LOG POPULATION**

Analysis will be performed overall and:

- by inclusion in the study (Yes vs. No). It is to be noted that due to patient anonymization it will not be possible to link patients listed in the screening log and patients included in the study; the number of patients included according to the screening log ('Chart entered to EDC=Yes') may not match with the number of patients actually included in the study according to eCRF. The variable 'Chart entered to EDC' from the screening log will be used to distinguish both of these groups.
- by reason for non-inclusion in the study (Did not meet selection criteria, Lack of time, Quotas were met, Other)

Characteristics of patients of the Eligible screening log population will be summarized using descriptive statistics for the following variables collected in the screening log: age at first Ozurdex implant injection (years), gender, anti-VEGF injections before the first Ozurdex implant injection (Yes, No), number of Ozurdex implant injections in each eye.

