## **15.0 ANALYSES OF THE OBJECTIVES OF THE STUDY**

### **15.1 ANALYSIS OF THE PRIMARY OBJECTIVE**

The primary objective '*To assess reinjection interval of Ozurdex implants in patients with DME in real-world in Germany and Switzerland*' will be assessed by the following outcomes:

- Total number of Ozurdex reinjections in the study eye during follow-up, and considering years after the first Ozurdex injection in the study eye (See definition in Table 21-1).
- Re[injection interval defined in months as: (Date of injection (j+1) – Date of injection j) ÷ (365.25÷12), for j=1,...,n where n is the number of reinjections in the study eye. The result will be rounded to 0.1.

The number of Ozurdex reinjections in the study eye per year will be first summarized using descriptive statistics for the following parameters:

- The total number and percentage of Ozurdex reinjections received during follow-up.
- Number and percentage (with 95% CI) of patients with at least one Ozurdex reinjection during Year 1 (See definition in Table 21-1), and number of reinjections per patient during Year 1, for all patients in the analysis population. Note: the first Ozurdex injection will not be considered here, only reinjections will be counted.
- Number and percentage (with 95% CI) of patients with at least one Ozurdex reinjection and number of reinjections per patient during Year k (k=2, 3), for patients having a complete Year k of follow-up (see definition of 'Complete year' in Section 21.2).
- Number and percentage of patients receiving each Ozurdex reinjection (first, second, third, etc) for each year of follow-up (Year k, k=1 to 3) considering patients having the complete year of follow-up.

The Ozurdex reinjection interval in the study eye will be described using descriptive statistics for the following parameters:

- Re[injection interval (months) considering all eligible reinjections recorded in the EDC. The 95% CI of the mean will also be presented.
- Re[injection interval (months) considering each reinjection separately (i.e. first reinjection, second reinjection, etc). 95% CI of the mean will also be presented.

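### The best-effort quota of anti-VEGF-naive patients may shift the unweighted overall mean reinjection interval away from routine practice, and no standardized mean is planned beside it

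*Protocol*

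**What the plan says.** Protocol 9.2 describes two streams of selection. The non-competitive stream takes eligible patients in order of first injection and stops at "approximately 70 patients in Germany and 30 patients in Switzerland". The competitive stream looks for patients without earlier anti-VEGF treatment. There, "sites will be asked to do their best to select a predetermined number of patients who do not meet this exclusion criteria", and "Recruitment of patients that are naïve to anti-VEGF treatment will stop when approximately 50 patients have been selected in Germany and Switzerland". The section closes with: "Overall, patient selection will stop when 150 patients have been selected for the study". The synopsis and Protocol 7.1 give 50 as a maximum for the naive group. Part of the competitive-selection text is redacted.

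SAP 15.1 describes the reinjection interval "considering all eligible reinjections recorded in the EDC. The 95% CI of the mean will also be presented". Neither document plans any weighting or standardization of this mean. Protocol 8.2, repeated in SAP 4.0, expects that "the results from this study may be generalizable to the overall population presenting with DME and treated with Ozurdex in Germany and Switzerland".

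Protocol 7.3.1.2 and SAP 7.0 present consecutive selection as the guard against patient selection bias. Neither mentions the naive quota.

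Two planned displays bear on the point. SAP Table 6-1 marks the primary objective for breakdown by naive status and by number of earlier anti-VEGF treatments, but the note under it lets a subgroup analysis be dropped when the group is too small. SAP 9.0 describes earlier anti-VEGF use (yes/no) in the eligible screening log population, split by inclusion in the study.

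**The concern.** In the competitive stream, naive status itself decides who is sampled. If naive status also predicts the interval, an unweighted mean over the combined sample answers a question about a mix fixed by design and not about the mix seen in practice.

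The protocol's own background makes both conditions plausible. Section 5.1 cites guidance that places corticosteroids mainly after anti-VEGF failure, with first-line use for particular groups. That suggests a natural naive share below one third, although no share is given. For the interval, the protocol cites 6.7 months in a one-year study of 27 treatment-naive patients (Sections 5.1 and 14.1). It also cites 4.7 and 4.9 months in two French databases that it does not describe as limited to naive patients (Section 14.1).

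The overall mean is the result on which the sample size was based. A shift in it is a bias, so more patients would not reduce it and the confidence interval would not show it.

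**Working it through.** **1. The plan's own precision.** Half-width = 1.96 × SD / √n with n = 150 (Protocol 14.1, Table 4). SD 1.5, 2.0, 2.5 and 3.0 months give 0.240, 0.320, 0.400 and 0.480 months. These round to the stated 0.2, 0.3, 0.4 and 0.5.

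**2. Shift of the unweighted mean.** Let w be the naive share in the sample, p the natural naive share among eligible patients, and d the difference in mean interval (naive minus pre-treated). The sample mean targets w·μN + (1−w)·μP and the practice mean is p·μN + (1−p)·μP. The difference between the two is (w − p) × d.

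- w: the consecutive stream gives 70 + 30 = 100 patients and the quota gives 50. If naive patients total 50, w = 50/150 = 0.333. If the 50 come on top of naive patients already among the 100, w = (50 + 100p)/150. The visible text does not settle which applies, so both are shown.
- p: not in the documents; assumed 5% to 40%.
- d: not in the documents; assumed 1 and 2 months. The cross-study contrast is 6.7 − 4.9 = 1.8 to 6.7 − 4.7 = 2.0 months, so 2 months is the upper end.

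| p | 50 naive in total: shift for d = 1 / 2 months | 50 on top: w, and shift for d = 1 / 2 months |
|---|---|---|
| 5% | 0.28 / 0.57 | 0.367; 0.32 / 0.63 |
| 10% | 0.23 / 0.47 | 0.400; 0.30 / 0.60 |
| 20% | 0.13 / 0.27 | 0.467; 0.27 / 0.53 |
| 30% | 0.03 / 0.07 | 0.533; 0.23 / 0.47 |
| one third | 0 / 0 | 0.556; 0.22 / 0.44 |
| 40% | −0.07 / −0.13 | 0.600; 0.20 / 0.40 |

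At 30.4375 days per month, the first shift column for p = 5-20% is 4 to 9 days for d = 1 and 8 to 17 days for d = 2. The plan states a precision of 6 to 15 days.

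**3. If the quota does not fill.** With 20 naive patients, w = 20/150 = 0.133. At p = 10% the shift is 0.03 months for d = 1 and 0.07 months for d = 2.

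**4. Pooling intervals instead of patients.** SAP 15.1 averages over reinjections, and patients with longer intervals contribute fewer of them. As an illustration, take 6.7 against 4.8 months (d = 1.9) with equal follow-up.

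- Sample share of intervals: (0.333/6.7) / (0.333/6.7 + 0.667/4.8) = 26%.
- Natural share of intervals at p = 10%: (0.1/6.7) / (0.1/6.7 + 0.9/4.8) = 7%.
- Shift, using the unrounded shares 0.264 and 0.074: (0.264 − 0.074) × 1.9 = 0.36 months. The patient-level formula gives (0.333 − 0.1) × 1.9 = 0.44.

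Pooling softens the shift but does not remove it.

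**5. Precision after standardizing.** Design effect = p²/w + (1−p)²/(1−w), at patient level with equal SD in both groups and w = 0.333.

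| p | Design effect | Half-width, SD 1.5 to 3.0 (months) | Increase |
|---|---|---|---|
| 20% | 1.080 | 0.25 to 0.50 | 4% |
| 10% | 1.245 | 0.27 to 0.54 | 12% |
| 5% | 1.361 | 0.28 to 0.56 | 17% |

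**The case against.** The strongest reply is that the size rests on two inputs the documents do not give. Protocol 5.1 also describes first-line use after major cardiovascular events or when monthly visits are refused, and it gives pseudophakia as a separate route to the indication. The natural naive share could therefore be near 30%, where the shift with 50 naive in total is at most 0.07 months. The 1.8 to 2.0 month contrast is between studies, not within one. The quota is best-effort and may stay unfilled. This all stands, and it makes the shift conditional.

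The plan is also not blind to the issue. Results by naive status and the log comparison would let a careful reader see both the mix and the stratum means. The study has no hypothesis, and the statement on generalizability is hedged. This stands in part: the displays reveal a distortion, but one of them is optional and neither corrects the overall mean.

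A reader might go further and infer that the screening log gives the true mix, so that a post-stratified mean by country should replace the primary estimate. The documents do not support that:

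- The eligibility rules for the log in SAP 6.1 do not require treatment for DME, although the log collects that item and Ozurdex has other approved indications (Protocol 5.1).
- The log's anti-VEGF item names no eye, while SAP 6.3 defines naive status for the study eye.
- Sites are only invited to complete the log.
- SAP 9.0 says log and eCRF cannot be linked, and that counts may differ.
- Splitting by country adds strata where Switzerland has only about 30 consecutive patients.

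**Conclusion.** The point holds as a conditional one. If the quota fills, about a third or more of the sample is naive by design, the overall mean carries that mix unweighted, and neither bias section says so. With 50 of 150 naive, an assumed natural share of 5-20% and a difference of 1 to 2 months, the patient-level shift is 0.13 to 0.57 months. That is comparable to the planned half-width of 0.24 to 0.48 months. It is somewhat smaller when intervals are pooled. It is near zero if the natural share is about 30% to one third (with 50 naive in total), if few naive patients are found, or if the intervals do not differ.

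A reader might infer that the headline mean mirrors the quota instead of practice, or describes no real population. That is not established, because neither the natural share nor the within-study difference is in the documents. What is supported is that the mean may reflect the quota, and that a cheap check on it is missing.

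**What to change.** 1. In SAP 15.1, keep the unweighted mean and add beside it an overall mean standardized to the naive and non-naive shares in the eligible screening log population, restricted to patients logged as treated for DME. State whether the weights refer to patients or to intervals, so that they match the estimand. The log also records the number of Ozurdex injections per eye, from which an approximate interval share can be formed. Record the addition in SAP 22.0.
2. Make the primary-objective display by naive status mandatory, exempt from the small-subgroup waiver under Table 6-1.
3. Name the quota as a source of selection bias in Protocol 7.3.1.2 and SAP 7.0, and qualify the generalizability statement in Protocol 8.2 and SAP 4.0 accordingly.

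**Cost.** This needs wording and a short piece of programming. No new data and no patient linkage are required, because only stratum shares are used. The half-width of the standardized mean is about 4%, 12% or 17% wider than that of the unweighted mean for natural shares of 20%, 10% or 5%. If the 50 come on top of naive patients among the 100, the design effects are 1.286, 1.375 and 1.432, and the increases about 13%, 17% and 20%. The weights are approximate, because log completion is by invitation and the anti-VEGF item does not specify the study eye. The standardized mean therefore belongs beside the primary estimate and should not replace it.

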## 10 STUDY ASSESSMENTS

This is a retrospective, observational study and patient data collected from the sites will be abstracted from medical charts. Baseline will be defined as the period prior to first Ozurdex implant injection (index event) and study period will be defined as the period between the first Ozurdex implant injection and 1 September 2018.

## 10.1 Data Collected in the Screening Log

Once a site has been initiated, site personnel will be invited to complete a screening log with all patients who received at least one Ozurdex implant injection. [REDACTED]

## 10.2 Demographics

Patients' age at first Ozurdex implant injection and gender will be recorded in the eCRF.

## 10.3 Medical and Ophthalmic History

Chronic medical conditions and medical conditions ongoing at time of first Ozurdex implant injection will be collected, along with year of onset. History of glaucoma, cataract and lens status (phakic or pseudophakic) will be collected.

DME history, i.e. date of onset of symptoms and date of DME diagnosis in the study eye, will be collected.

## 10.4 Prior and Concomitant Treatments

### 10.4.1 Prior and Concomitant Cataract and Glaucoma Procedures

Cataract and glaucoma procedure performed on the study eye prior to the study period and during the study period will be recorded (e.g., cataract surgery, glaucoma laser, trabeculectomy, glaucoma valve implant, laser peripheral iridotomy, other procedures).

### 10.4.2 Prior and Concomitant Laser Therapy

Focal/grid laser treatments for DME occurred on the study eye prior to the study period and during the study period will be recorded (date of treatment, focal or grid laser photocoagulation).

#### **10.4.3 Prior and Concomitant Other Intravitreal Injections**

Intravitreal injections other than Ozurdex received prior to study period will be recorded for the study eye: name, number of treatments, and last treatment date.

At each visit occurred during the study period, intravitreal injections other than Ozurdex received in the study eye will be recorded.

Special focus will be placed on the following intravitreal injections:

- Anti-VEGF therapies such as Lucentis®, Eylea®, and Avastin®
- Corticosteroid therapies other than Ozurdex such as Iluvien® and triamcinolone

#### **10.4.4 Concomitant Medications**

A pre-defined list of concomitant medications that may have an impact on short term efficacy and safety of the drug received at time of first Ozurdex implant administration and during the study period will be recorded (inclusive of IOP medications, corticoid medications, non-steroid anti-inflammatory drug, immunosuppressive drug, and antithrombotic agents) : medication name, start date, end date, indication (eye condition vs. other medical condition).

### **10.5 Clinical Examinations**

Biomicroscopic and ophthalmomicroscopic exams performed in the study eye (yes/no), and intraocular pressure value measured in the study eye will be collected at baseline and at each visit occurred during the study period.

### **10.6 Contralateral Eye**

DME status in the contralateral eye will be recorded at baseline and at all visits occurred during the study period.

Treatments for DME received prior to study period will be recorded for the contralateral eye. For each visit occurred during the study period, treatments received in the contralateral eye (inclusive of intravitreal treatment) will be recorded.

### **10.7 Ozurdex Implants**

For each Ozurdex implant injection performed in the study eye, date of injection will be recorded. If available, reason for initial injection and reinjections will be collected.

### **10.8 Effectiveness Assessments**

#### **10.8.1 Best Corrected Visual Acuity**

BCVA will be collected at baseline and at all visits during the study period in both study and contralateral eyes. Values will be recorded in the eCRF according to local practice (Snellen, MAR, EDTRS, etc.) along with scale name or method used to assess BCVA.

#### **10.8.2 Central Retinal Thickness**

CRT measured in the study eye will be collected at baseline and at all visits during the study period if it was measured using OCT. Technology and device brand used to measure OCT will also be collected.

## 10.9 Safety Assessments

### 10.9.1 Definitions

#### 10.9.1.1 Adverse Events

An **Adverse Event (AE)** is defined as any untoward medical occurrence in a patient or clinical trial subject administered a medicinal product and which does not necessarily have a causal relationship with this treatment. An AE can therefore be any unfavorable and unintended sign (including an abnormal laboratory finding), symptom, or disease temporally associated with the use of a medicinal product, whether or not the event is considered causally related to the use of this medicinal product (see GVP Annex IV, ICH-E2D guideline).

#### 10.9.1.2 Adverse Reactions

An **adverse reaction** is a response to a medicinal product which is noxious and unintended [DIR2001/83/EC Art 1(11)] (see GVP Annex I, Definitions). Synonyms are adverse drug reactions (ADR), suspected adverse (drug) reaction, adverse effect, and undesirable effect. Response in this context means that causal relationship between the medical product and an AE is at least a reasonable possibility (see Annex IV, ICH-E2A Guideline 5). Adverse reactions may arise from use of the product within or outside the terms of the marketing authorization or from occupational exposure. Conditions of use outside the marketing authorization include off-label use, overdose, misuse, abuse and medication errors.

For regulatory reporting purposes on post approval safety data, if an AE is spontaneously reported, even if the relationship is unknown or unstated, it meets the definition of an ADR.

#### 10.9.1.3 Serious Adverse Drug Reactions

An SADR is an ADR that meets any of the following criteria (see GVP Annex IV, ICH-E2A Guideline 5):

- Results in **Death** of patient.
- Is **life-threatening**: this refers to an event/reaction in which the patient was at risk of death at the time of the event/reaction; it does not refer to an event/reaction which hypothetically might have caused death if it were more severe.
- Requires **inpatient hospitalization**: An event/reaction that results in an admission to the hospital for any length of time. This does not include an emergency room visit or admission to an outpatient facility.
- Results in **prolongation of existing hospitalization**: An event/reaction that occurs while the study patient is hospitalized and prolongs the patient's hospital stay.
- Is a **congenital anomaly/birth defect**: An anomaly detected at or after birth, or any anomaly that results in fetal loss.
- Results in **persistent or significant disability/incapacity**: An event/reaction that results in a condition that substantially interferes with the activities of daily living of a study patient. Disability is not intended to include experiences of relatively minor medical significance such as headache, nausea, vomiting, diarrhea, influenza, and accidental trauma (e.g., sprained ankle).

- Is a **medically important event or reaction**: An important medical event/reaction that may not be immediately life-threatening or result in death or hospitalization, but based on medical judgment may jeopardize the patient and may require medical or surgical intervention to prevent any of the outcomes listed above (i.e., death of patient, life-threatening, hospitalization, prolongation of hospitalization, congenital anomaly/birth defect, or persistent or significant disability/incapacity). Examples of such events include allergic bronchospasm requiring intensive treatment in an emergency room or at home, blood dyscrasias or convulsions that do not result in inpatient hospitalization, or the development of drug dependency or drug abuse.
- Any **suspected transmission via a medicinal product of an infectious agent** is also considered as a SADR

#### **10.9.1.4 Adverse Events of Special Interest**

An AE of special interest (AESI) (serious or non-serious) is an AE specific to the sponsor's product or program. Such an event might warrant further investigation to characterize and understand it.

#### **10.9.2 Collection and reporting of Safety Events by Investigators**

The study will be conducted in accordance with Directive 2001/83/EC, Regulation (EC) No 726/2004, Commission Implementing Regulation (EU) No 520/2012 as amended and detailed in GVP Modules VI.

Considering that study aims to explore the potential impact of recurrent Ozurdex injections, and not confirm the whole safety profile, and considering the current knowledge of the study drug safety profile, this study focuses only on the following AESIs (related or not to Ozurdex):

- **Glaucoma**, defined as damage to the optic nerve with progressive vision loss (open angle glaucoma, normal tension glaucoma, and acute angle closure glaucoma)
- **Intraocular hypertension**, defined as IOP without meeting the criteria for glaucoma
- **Hypotony**, defined as low IOP  $\leq 5$  mmHg
- **Cataract or lens opacities** (nuclear sclerotic, cortical and posterior subcapsular)
- **Ocular bleeding or hemorrhage** (conjunctival, anterior chamber, vitreous, macular, retinal)
- **Retinal detachment, tear or hole**
- **Vitreous detachment**
- **Infection vs. Non-infection related Ocular inflammation** (conjunctivitis, blepharitis, episcleritis, scleritis, keratitis, uveitis, retinitis and endophthalmitis)
- **Significant vitreous loss**
- **Mechanical failure of device and implant misplacement**
- **Implant dislocation**

In addition to AESIs, off-label use should be collected, and reported to Allergan whether or not off-label use was associated with an AE.

Due to the retrospective design of the study, the reporting of safety events to the sponsor is not solicited for this study. However, investigators are reminded about the possibility for them to report

any suspected ADRs directly to the marketing authorization holder of the suspected medicinal product (studied or not) or to the concerned competent authority via the national spontaneous reporting system.

